    - The proportion of patients who discontinue to facitinib after developing  $\geq 1$  VTE risk factor while taking to facitinib; and
    - The proportion of patients who continue taking tofacitinib after developing  $\geq 1$  VTE risk factor while taking tofacitinib;
  - Use in patients aged 65 years and older, as measured by:
    - The proportion of patients 65 years and older with no alternative treatments *prior to* initiation of tofacitinib, reported overall and by approved indication;

- The proportion of patients aged 65 years, receiving tofacitinib, who have 0 prescription dispensings of tofacitinib from the time they turn 65.5 years old through to the end of the follow-up period, reported overall and by approved indication;
- The proportion of patients aged 65 years, receiving tofacitinib, who have ≥1 prescription dispensing of tofacitinib from the time they turn 65.5 years old through to the end of the follow-up period and no history of alternative treatments *prior to* that tofacitinib prescription dispensing, reported overall and by approved indication; and
- The proportion of patients aged 65 years, receiving tofacitinib, who have ≥1 prescription dispensing of tofacitinib from the time they turn 65.5 years old through to the end of the follow-up period and a history of alternative treatments *prior to* that tofacitinib prescription dispensing, reported overall and by approved indication;
- Use in patients with CV risk factors, as measured by:e
  - The proportion of patients with evidence of  $\geq 1$  CV risk factors *prior to* initiation of tofacitinib, reported overall and by approved indication;
  - The proportion of patients with evidence of ≥1 CV risk factors *prior to* initiation of tofacitinib and no prior use of an alternative therapy (i.e., biologic), reported overall and by approved indication;
  - The proportion of patients who discontinue to facitinib after developing  $\geq 1$  CV risk factor while taking to facitinib; and
  - The proportion of patients who continue taking tofacitinib after developing ≥1 CV risk factor while taking tofacitinib;
- Use in patients with malignancy risk factors, as measured by:e
  - The proportion of patients with evidence of  $\geq 1$  malignancy risk factors *prior to* initiation of tofacitinib, reported overall and by approved indication;

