Age at tofacitinib initiation	Demographic	Calculated as the date of tofacitinib initiation minus the patient's year of birth and reported in the following categories: <18 years, 18-29 years, 30-39 years; 40- 49 years; 50-59 years; 60-69 years; 70-79 years; and $\geq$ 80 years; and <65 years and $\geq$ 65 years.		
Sex	Demographic	Reported in the following categories: Male, Female, and Unknown. Assessed on the date of the index tofacitinib prescription dispensing.		

 Table 3.
 Operational definitions of study variables in the selected databases

m In GKV claims, outpatient diagnoses are reported quarterly.

n In the PHARMO Database Network, the high-budget impact medication dataset contains only declared medication for approved indications. It might not be possible to determine off-label use in this dataset.

Variable	Role	Operational definition
Hepatic impairment	Comorbidity	Defined as ≥1 ICD-10 diagnosis code for hepatic impairment.
Hepatic impairment, mild or moderate o	Comorbidity	Defined as ≥1 ICD-10 diagnosis code for mild or moderate hepatic impairment.
Hepatic impairment, severe o	Comorbidity	Defined as ≥1 ICD-10 diagnosis code for severe hepatic impairment.
Renal impairment	Comorbidity	Defined as ≥1 ICD-10 diagnosis code for renal impairment or a combination of ICD-10 diagnosis codes and/or ICD-10 procedure codes.
Renal impairment, mild o	Comorbidity	Defined as ≥1 ICD-10 diagnosis code for mild renal impairment or a combination of ICD-10 diagnosis codes and/or ICD- 10 procedure codes.
Renal impairment, moderate o	Comorbidity	Defined as ≥1 ICD-10 diagnosis code for moderate renal impairment or a combination of ICD-10 diagnosis codes and/or ICD-10 procedure codes.
Renal impairment, severe o	Comorbidity	Defined as ≥1 ICD-10 diagnosis code for severe renal impairment or a combination of ICD-10 diagnosis codes and/or ICD- 10 procedure codes.
Herpes zoster (HZ)	Comorbidity	Defined as $\geq 1$ ICD-10 diagnosis code for HZ.
Human immunodeficiency virus (HIV)	Comorbidity	Defined as ≥1 ICD-10 diagnosis code for HIV.
Tuberculosis (TB), including both active and latent TB p	Comorbidity	Defined as ≥1 ICD-10 diagnosis code for TB.
Viral hepatitis B or C	Comorbidity	Defined as ≥1 ICD-10 diagnosis code for viral hepatitis B or C.

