Continuation of tofacitinib after developing ≥1 VTE risk factors while taking tofacitinib	Outcome: VTE risk factor	Defined as $\geq 1$ VTE risk factor while receiving tofacitinib therapy (as listed and defined above) PLUS $\geq 1$ prescription dispensing for tofacitinib within a specific time window after the code for the VTE risk factor.
		Note: The time window for when to look for a tofacitinib prescription dispensing will be specific to the VTE risk factor acquired while receiving tofacitinib therapy and will be operationalized during SAP development.
		Duration of tofacitinib therapy defined in Section 9.3.3.
Compliance to recommend	lations for limitations of use in patie	nts aged 65 years and older
Initiating tofacitinib with no prior use of an alternative therapy (i.e., biologic) among patients 65 years of age and older	Outcome: Age 65 years and older	Defined as patients who are 65 years and older on the date of the index tofacitinib dispensing with 0 prescription dispensings for a biologic (as identified by ATC codes) in the 12 months prior.
		Complete list of biologics in ANNEX 6. LIST OF ATC CODES FOR MEDICATIONS OF INTEREST TO AVOID WHILE TAKING TOFACITINIB.

Table 3.	Operational	definitions of	fstudy	variables in	the selected	databases
----------	-------------	----------------	--------	--------------	--------------	-----------

Variable	Role	Operational definition
Discontinuation of tofacitinib for patients who turn 65 years old while receiving tofacitinib	Outcome: Age 65 years and older	Defined as patients aged 65 years, receiving tofacitinib, who have 0 prescription dispensings of tofacitinib from the time they turn 65.5 years old through to the end of the follow-up period.
		Note: Patients have 6 months to discontinue tofacitinib to allow them time to be seen by their healthcare provider.
		Duration of tofacitinib therapy defined in Section 9.3.3.
Inappropriate continuation of tofacitinib for patients who turn 65 years old while receiving tofacitinib	Outcome: Age 65 years and older	Defined as patients aged 65 years, receiving tofacitinib, who have $\geq 1$ prescription dispensing of tofacitinib from the time they turn 65.5 years old through to the end of the follow-up period and 0 prescription dispensings for a biologic (as identified by ATC codes) prior to that tofacitinib prescription dispensing.

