#### 9.7.1.2.2.1.2. Patients aged 65 years and older

The proportion of patients initiating tofacitinib aged 65 years and older at the index date without prior alternative therapy (defined as  $\geq 1$  biologic in the 12 months prior to index date), will be described and tabulated. Proportions will be presented overall and stratified by approved indication.

The proportion of patients aged 65 years, receiving tofacitinib, who have 0 prescription dispensings of tofacitinib from the time they turn 65.5 years old through the end of the follow-up period, will be described and tabulated. Proportions will be presented overall and stratified by approved indication.

The proportion of patients aged 65 years, receiving tofacitinib, who have  $\geq 1$  prescription dispensing of tofacitinib from the time they turn 65.5 years old through the end of the follow-up period and no history of alternative treatments *prior to* that tofacitinib prescription dispensing, will be described and tabulated. Proportions will be presented overall and stratified by approved indication.

The proportion of patients aged 65 years, receiving tofacitinib, who have  $\geq 1$  prescription dispensing of tofacitinib from the time they turn 65.5 years old through the end of the follow-up period and a history of alternative treatments *prior to* that tofacitinib prescription dispensing, will be described and tabulated. Proportions will be presented overall and stratified by approved indication.

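### The outcomes for patients who reach 65 on tofacitinib are defined so that patients who start at 65 also enter, and some of those can never be classed as discontinued

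*Protocol*

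**What the plan says.** In Section 9.3.2, Table 3, the first of the three rows is labelled "Discontinuation of tofacitinib for patients who turn 65 years old while receiving tofacitinib". The other two, inappropriate and appropriate continuation, carry the same population in their labels: "tofacitinib for patients who turn 65 years old while receiving tofacitinib". Each row has a note explaining the half-year allowance: "Patients have 6 months to discontinue tofacitinib to allow them time to be seen by their healthcare provider".

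The definition cells use a different population. Discontinuation is "Defined as patients aged 65 years, receiving tofacitinib, who have 0 prescription dispensings of tofacitinib from the time they turn 65.5 years old", counted to the end of follow-up. The two continuation rows use the same opening and require at least one "prescription dispensing of tofacitinib from the time they turn 65.5 years old through to the end of the follow-up period". They are separated by whether a biologic was dispensed beforehand.

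Section 9.3.1 (among the primary outcomes, and again among the secondary ones by reporting period) and Section 9.7.1.3.2 use only the wording of the definition cells, as does Section 9.7.1.2.2.1.2: "The proportion of patients aged 65 years, receiving tofacitinib, who have 0 prescription dispensings of tofacitinib from the time they turn 65.5 years old". None of them repeats the label's condition.

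Section 9.2.3 sets the index date at the first dispensing in the indexing period and starts the 12-month follow-up on that date. Table 3 also has a separate outcome for patients aged 65 or older at index with no biologic in the preceding 12 months.

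**The concern.** The label describes patients already on treatment at their 65th birthday. The definition admits anyone who is 65 and on the drug, including people whose first dispensing came after that birthday. The 6-month note makes sense only for the first group.

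For the second group the rule misfires. A patient first dispensed at 65.7 has a dispensing after 65.5 simply by having an index date, and so is a continuer even without a refill. Whether that patient is an appropriate or inappropriate continuer depends only on prior biologic use, which largely repeats the initiation outcome. A patient starting at 65.2 has 0.3 years, or 3.6 months, before the count begins.

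At stake are three primary proportions and their versions in six reporting periods (three VTE, three CV and malignancy). They would mix a question about starting treatment with one about carrying on past a birthday.

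**Working it through.** **The plan's own figure.** The protocol gives no figure for this outcome. Its one design figure, in Section 9.5, reproduces: 0.50 × 0.50 × 1.96² / 0.10² = 96.04, rounded up to 97 and set at 100 per indication and country. It covers patients of all ages and is not in dispute.

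**Classification by index age.** Inputs are the Table 3 rule and the 12-month follow-up of Section 9.2.3.

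- Index age 64.0 to under 64.5: follow-up ends before 65.5 (64.4 + 1 = 65.4). A patient who reaches 65 on the drug has no dispensing after 65.5 and counts as discontinued whatever happens.
- Index age 64.5 to under 65.0: the intended group. The patient can reach 65 on the drug, has the full 6 months, and follow-up passes 65.5.
- Index age 65.0 to under 65.5: a new starter, with 65.5 minus index age to stop, which falls from 6 months towards 0.
- Index age 65.5 to under 66: a new starter whose index dispensing meets the continuation rule. The probability of being classed as discontinued is exactly 0.
- Index age 66 or over: not 65 years of age, so outside the rule.

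This step needs no assumption.

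**Illustrative size.** The assumptions, none from the documents, are index age uniform over 64 to 66, monthly dispensing while on the drug, exponential time to stopping, and 12-month persistence of 100%, 80%, 60% or 40%. Under these, by simulation:

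| 12-month persistence | Starters at 65, share of literal denominator | Started at 65.5 to 66 (forced continuers) | Discontinued, literal rule | Discontinued, only those reaching 65 on the drug | Of those, cannot reach 65.5 | Discontinued, reached 65 on the drug and follow-up reaches 65.5 |
|---|---|---|---|---|---|---|
| 100% | 50.0% | 25.0% | 29.2% | 58.3% | 49.9% | 16.7% |
| 80% | 52.7% | 26.4% | 30.3% | 60.6% | 47.1% | 25.4% |
| 60% | 56.1% | 28.1% | 31.8% | 63.6% | 43.6% | 35.5% |
| 40% | 60.4% | 30.2% | 33.7% | 67.7% | 38.7% | 47.3% |

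The first row can be checked by hand. With full persistence the last monthly dispensing falls 11/12 year after index, so index ages from 64 to 64.583 show none after 65.5. Over the two-year span that is 0.583/2 = 29.2%; among index ages 64 to 65 it is 58.3%; among index ages 64.5 to 65 it is 0.083/0.5 = 16.7%.

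**What the table shows.** Two opposite distortions operate. Forced continuers lower the discontinued share, and patients indexed at 64.0 to 64.5 raise it. As persistence falls from 100% to 40%, the literal proportion moves 33.7 − 29.2 = 4.5 points, while the proportion in the intended, assessable group moves 47.3 − 16.7 = 30.6 points. The literal figure is higher than that group's at 100% and 80% persistence and lower at 60% and 40%. Removing starters alone gives 58% to 68%, mostly because 39% to 50% of the remaining patients cannot reach 65.5.

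**The case against.** The best defence is that Table 3 already states the restriction. The labels, the 6-month note and the words discontinuation and continuation all presuppose earlier use, Section 9.3.1 refers to Table 3 for definitions, and Section 9.3.2 says final algorithms will be refined in the SAP. Read as a whole row, a starter at 65.7 is out of scope, and a true turner's index dispensing can never fall after 65.5.

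This shows the intent, and a careful programmer might follow it. It does not remove the conflict, because the definition cells and the analysis sections state a different population. For the VTE, CV and malignancy outcomes Table 3 expressly leaves the discontinuation windows to the SAP; here it fixes the 65.5 rule. Section 9.7 adds that major changes to primary endpoint definitions belong in a protocol amendment.

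Other parts of the defence stand. A reader might infer that one prescribing decision is counted twice as non-compliance. The outcomes are separately tabulated proportions with no composite, and the overlap concerns only starters without a prior biologic. A reader might also infer that the 65.5-year date cannot be located, because Table 3 has age "Calculated as the date of tofacitinib initiation minus the patient's year of birth". That formula is given for age at initiation only, and no current data-source description says that only year of birth is held.

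**Conclusion.** The concern holds as a conflict between label and definition. Followed literally, the rule admits starters at 65, makes discontinuation impossible for those starting between 65.5 and the 66th birthday, and shortens the allowance for those starting between 65.0 and 65.5. This rests only on the wording and on follow-up starting at index.

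The shares of 50% to 60% and 25% to 30% are illustrations under assumed ages and persistence. The stronger conclusion that discontinuation is biased downward is not supported: the two distortions oppose each other and the net sign changes with persistence. Nor do the documents show that new starters were meant to be included; the label and note point the other way.

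**What to change.** In Table 3 (Section 9.3.2) and Sections 9.3.1, 9.7.1.2.2.1.2 and 9.7.1.3.2, make the population of all three outcomes: index date before the 65th birthday and on therapy at that birthday. A separate rule to ignore the index dispensing is then unnecessary. Starters at 65 or older remain in the existing initiation outcome.

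In the same change, limit the denominator to patients whose 12-month follow-up extends past 65.5, that is, index age about 64.5 to under 65, and report the others as not assessable. The SAP can set the margin past 65.5 so that at least one further dispensing would fall due; the 16.7% at full persistence arises because some patients have none.

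Where a database holds only year of birth, report these outcomes as not assessable. For birth year Y, being certainly under 65 at index requires an index date before 1 January of Y+65, so follow-up ends by about the start of Y+66. Being certainly past 65.5 requires about July of Y+66. No patient meets both.

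The cost is a wording change before data extraction (estimated start 30 September 2022) and a smaller denominator with wider intervals. Section 9.5 already accepts that precision will vary by outcome. No clinical rule on stopping treatment is affected; only the outcome's label and definition need to be reconciled.

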The sub-objective that evaluates "prescribers' adherence to the tofacitinib aRMMs, specifically, compliance to patient screening and laboratory monitoring prior to and during tofacitinib treatment" will *not* be assessed in Sweden because the Swedish national health registers do not capture the laboratory tests of interest. In GKV claims, it may not be possible to differentiate an absolute lymphocyte count (ALC) laboratory test from an absolute neutrophil count (ANC) laboratory test, or an alanine aminotransferase (ALT) laboratory test from an aspartate aminotransferase (AST) laboratory test. In the PHARMO Database Network, tuberculosis (TB) screening and viral hepatitis B and C testing are not captured.

**Study design:** This will be a descriptive drug utilisation study using secondary data collected from databases in Sweden, Hungary, the Netherlands, and Germany. The study observation period will be 01 April 2016 through 31 December 2024. All results will be stratified by study country and approved indication (i.e., RA, PsA, and UC).

**Population:** Patients will be included in the study if they have  $\geq 1$  prescription dispensing of tofacitinib during the indexing period, 12 months of available medical history before and 12 months after the index tofacitinib dispensing, and 0 prescription dispensings of tofacitinib in the 12 months prior to the indexing period.

**Variables:** Demographic characteristics (age, sex), diagnoses (indication [including off-label indications], comorbidities, contraindicated use, VTE risk factors, CV risk factors, malignancy risk factors), patients 65 years and older with no alternative treatments prior to initiation of tofacitinib, prior and current medications, procedures (including screening and monitoring tests), ADD, and duration of tofacitinib therapy will be examined.

**Data sources:** This study will use the Swedish national health registers: National Patient Register (NPR), the Swedish Prescribed Drug Register (PDR), the Swedish Medical Birth Register (MBR), the Swedish National Cancer Registry (NCR), and the Swedish Cause of Death Register; in Hungary, the National Health Insurance Fund Administration (NHIFA), an administrative claims database; in the Netherlands, the PHARMO Database Network, a population-based network of electronic healthcare databases; and in Germany, GKV claims, an administrative claims database.

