# Figure 4. Example index tofacitinib dispensing and patient-specific study period against the VTE Reporting Periods

The 12-month **baseline period** will immediately precede the patient's index date and will be used to ascertain indication (including off-label indications), comorbidities, prior and current medications, potential contraindicated use of tofacitinib, VTE risk factors, use in patients aged 65 years and older, CV risk factors, malignancy risk factors, and whether there is evidence that prescribers are following the recommended screenings in the aRMM materials that should occur *prior to* initiation of tofacitinib.

The 12-month **follow-up period** will begin on the patient's index date and will be used to ascertain comorbidities, comedications, compliance to the recommended posology per indication (ADD) and duration of tofacitinib treatment, potential contraindicated use of tofacitinib, VTE risk factors, CV risk factors, malignancy risk factors, use with concomitant medications not compatible with tofacitinib, and whether there is evidence that prescribers are following the recommended monitoring in the aRMM materials that should occur *after* initiation of tofacitinib.

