### 9.3.2. Variable definitions

Table 3 summarises and defines the study variables to be collected and analysed in the selected databases. Unless otherwise specified, these variables will be assessed during each patient's entire study period, baseline period, and follow-up period.

This study will use code-based algorithms from the literature (validated against a gold standard measure, where possible) and/or other code lists to identify study variables. All code-based algorithms and code lists will be reviewed and/or approved by the study sponsor

prior to study initiation. Preliminary algorithms and/or codes are proposed in the following table (see also ANNEX 3 through ANNEX 7). Final algorithms and/or code lists will be refined as part of the SAP development.

Where possible, operational definitions for the variables listed in Table 3 will be similar across the databases. Only ICD-10 diagnosis codes and procedure codes are referenced in Table 3; the specific coding systems used in each data source will be further described in the SAP. See Section 9.4 (Data sources) for a description of the selected databases and Section 9.9 (Limitations of the research methods) for a summary of the limitations associated with these databases.

Variable	Role	Operational definition		
Indication m				
Indication n	Indication (including potential off-label indications)	Reported in the following categories: RA, PsA, UC, and Other / unknown (i.e., potential off-label indications).		
		Defined as $\geq 1$ International Classification of Disease, 10 th Revision (ICD-10) diagnosis code for RA, PsA, or UC in the 12 months prior to and including the day of tofacitinib initiation. If there is no ICD-10 diagnosis code in the patient's data for RA, PsA, or UC during this time period, then the indication will be reported as Other / unknown. If a patient has multiple codes for any combination of indications (e.g., RA and PsA), the ICD-10 diagnosis code closest to the index tofacitinib prescription dispensing will be used to determine indication.		
Primary Objective 1: Demo	Primary Objective 1: Demographics, comorbidities, and prior and current medications m			

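### Patients who start tofacitinib before age 64.5 are never observed at 65.5, yet the turning-65 outcomes can only count them as having discontinued

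*Protocol*

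**What the plan says.** Section 9.3.2 (Table 3) has three outcomes for patients who reach 65 on treatment: discontinuation, inappropriate continuation and appropriate continuation. The first row is labelled "Discontinuation of tofacitinib for patients who turn 65 years old while receiving tofacitinib" and its definition begins "Defined as patients aged 65 years, receiving tofacitinib, who have 0 prescription dispensings of tofacitinib from the time they turn 65.5 years old". The analysis text in Section 9.7.1.2.2.1.2 repeats the rule: patients "who have 0 prescription dispensings of tofacitinib from the time they turn 65.5 years old through the end of the follow-up period". Both continuation rows need at least one dispensing from 65.5 onward and differ only in whether a biologic was dispensed beforehand. A note explains the half-year: "Patients have 6 months to discontinue tofacitinib to allow them time to be seen by their healthcare provider".

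The Abstract requires "12 months of available medical history before and 12 months after the index tofacitinib dispensing". Section 9.2.3 fixes the follow-up period at 12 months, and the text under Figure 4 says that it "will begin on the patient's index date".

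The same outcomes appear in Section 9.3.1 under primary objective 2. Section 9.7.1.3.2 repeats them for three VTE and three CV and malignancy reporting periods.

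**The concern.** The half-year allowance runs from the 65th birthday, but the observation clock runs from the index dispensing. A patient who starts treatment well before 65 uses up most of the 12 months before the birthday, and follow-up then closes before the allowance ends. The definition does not separate a patient seen after 65.5 with no dispensing from one not seen after 65.5 at all. Both continuation categories need a dispensing after 65.5, so the unseen patient can fall only into discontinuation.

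The discontinuation proportion would then mix prescriber behaviour with where the index date happened to fall relative to the birthday. It is a primary-objective-2 result and is also meant to show change after the revised risk minimisation materials.

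**Working it through.** The protocol states no expected proportion for this outcome, so there is no figure to reproduce.

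**Inputs from the protocol:** cut at 65.5 (Table 3); follow-up of 1 year from index (Section 9.2.3); population that turns 65 on treatment (Table 3 row label).

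**Assumed, because the protocol gives no figure:** index age uniform within 64-65; a constant stopping hazard equivalent to 0-60% per year; dispensings every 30 or 90 days from index.

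**1. Length of the window.** For index age *a*, age 65.5 is reached 65.5 − *a* years after index, and follow-up ends at 1 year. Time observed after 65.5 = 1 − (65.5 − *a*) = *a* − 64.5 years. At *a* = 64.2 this is −0.3, so there is no window. At *a* = 64.8 it is 0.3 years. For anyone under 65 at index it is below 0.5 years.

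**2. Share with no window, by the row label (index age 64 to 65).** With annual stopping *s*, write *r* = √(1 − *s*). Patients still on drug at their 65th birthday are weighted by (1 − *s*)^*u*, where *u* is the time from index to that birthday. Those with no window have *u* ≥ 0.5. The ratio of the two integrals simplifies to *r*/(1 + *r*).

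| Annual stopping | *r* | No window, *r*/(1 + *r*) | Labelled discontinued, rule as written | Of all patients: on drug at month 12 but labelled discontinued | Labelled discontinued, only those observed past 65.5 |
|---|---|---|---|---|---|
| 0% | 1.000 | 50.0% | 51% | 51% | 3% |
| 20% | 0.894 | 47.2% | 55% | 46% | 14-15% |
| 30% | 0.837 | 45.6% | 56-58% | 43% | 20-22% |
| 40% | 0.775 | 43.6% | 58-60% | 39% | 26-29% |
| 50% | 0.707 | 41.4% | 61-63% | 36% | 33-37% |
| 60% | 0.632 | 38.7% | 64-66% | 31% | 40-45% |

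The last three columns come from simulation, one million patients per scenario; ranges span 30- and 90-day dispensing. The 0% row can be checked by hand. With either interval the last dispensing is on day 360, and 65.5 falls uniformly between 0.5 and 1.5 years after index, so the share is 1.5 − 360/365 = 51.4%.

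**3. Non-uniform index age.** With density 1 + *k*(*x* − 0.5) across the year and nobody stopping, the no-window share is 0.5 − *k*/8. For *k* = ±0.3 this is 46-54%.

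**4. Wider reading.** Suppose patients already 65 at index also count. With nobody stopping, the share is 0.5/1.5 = 33% (index age 64-65.5) or 0.5/2 = 25% (64-66). At 50% annual stopping the hazard is 0.693. The no-window part is (0.707 − 0.5)/0.693 = 0.299, and the part turning 65 on drug is 0.5/0.693 = 0.721. The shares are 0.299/1.221 = 24% and 0.299/1.721 = 17%.

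**5. Dilution of change.** If half the denominator is fixed at discontinued, a true rise from 10% to 50% among observable patients is reported as 0.5 + 0.5 × 0.10 = 55% rising to 0.5 + 0.5 × 0.50 = 75%. That is 20 points instead of 40.

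**The case against.** **It may be left to the SAP.** Section 9.3.2 says "Final algorithms and/or code lists will be refined as part of the SAP development", and Section 9.3.3 defers details of treatment duration. But for VTE, CV and malignancy risk factors Table 3 expressly leaves the look-forward window to the SAP, whereas for the age outcomes it fixes the window itself. Neither deferral announces a rule on reaching 65.5, and Section 9.9 does not list the problem.

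**The size is easy to overstate.** A reader might infer that at least half are misclassified by construction. That needs uniform index age, no stopping before 65, and a population limited to index ages 64-65. The protocol supplies none of the first two, and its definition (aged 65, receiving tofacitinib) is looser than its row label. A figure near 62% for 90-day packs can be reached by letting refill timing be random relative to index, but the index date is itself a dispensing, so regular refills have a fixed phase.

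**Discontinued is not the same as compliant.** A reader might infer that the study would report high compliance whatever prescribers did. Continuers with a prior biologic are already classed as appropriate, so moving them to discontinuation mislabels them without raising overall compliance. Only continuers without a prior biologic inflate it.

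**The impact has limits.** The study is descriptive, and the outcome on starting at 65 or older without a prior biologic is not affected by the empty window. If index-age and persistence patterns are stable, the error recurs similarly in each period. It then inflates levels and dilutes change, and does not create a false trend.

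**Year of birth.** Table 3 gives age at initiation as "Calculated as the date of tofacitinib initiation minus the patient's year of birth". No section says how 65.5 is dated, and the source descriptions do not say that only the birth year is held. This is a secondary point, resting on inference.

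All of these limits stand except the first. None gives a patient indexed before 64.5 a window.

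**Conclusion.** The defect holds and follows from the protocol's own definitions: every patient indexed before 64.5 who counts towards these outcomes is recorded as discontinued without being observed at 65.5. Under the row label and uniform index age, the share with no window is 50% if nobody stops before 65 and about 39-47% at 20-60% annual stopping. It is roughly 17-33% if patients already 65 at index are admitted (0-50% annual stopping). These figures depend on assumed age and persistence; the empty window does not.

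The discontinuation proportion is inflated, and the two continuation proportions combined fall by the same amount, each taking only part of it. Under the label's reading the total labelled discontinued is 51-66% in all the uniform scenarios, but part of that is true stopping. The documents therefore do not support a claim that at least half are wrongly classified, or that all of them are counted as compliant.

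**What to change.** Amend Table 3 and Sections 9.3.1, 9.7.1.2.2.1.2 and 9.7.1.3.2 in one of two ways:

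- Restrict the denominator of all three outcomes to patients whose follow-up extends past 65.5 by at least one dispensing interval. Restricting to those observed past 65.5 already cuts false discontinuation from about 51% to about 3% when nobody stops. Requiring a full interval removes the rest for regular refills.
- Or use one fixed window length after 65.5, the same for every patient and reporting period, drawn from data already within the observation period. Following everyone to 31 December 2024 would not do, because observation time would then differ widely between early and late indexers.

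Under either option, report the number not assessable separately. Reconcile the row label with the definition, so that it is clear whether patients already 65 at index belong. Date 65.5 from the full or month-level birth date where the source holds it, since age from birth year alone cannot resolve a half-year cut. The six-month allowance itself need not change.

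The cost is an edit to wording and smaller denominators. Under the first option and the row label, the remaining windows are under six months. Under the second, some late-2023 indexers stay unassessable: one aged 64.0 at a December 2023 index reaches 65.5 in mid-2025, after the data end.
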